8. RESEARCH QUESTIONS AND OBJECTIVES

The aim of the study is to assess the long-term (548 days) real-world utilization patterns of Mysimba/Contrave use among patients who are prescribed Mysimba/Contrave. There are no a priori hypotheses for this study.

The primary objectives of the study are:

- To describe demographic and baseline characteristics of patients initiating use of Mysimba/Contrave; and
- 2. To evaluate patterns of Mysimba/Contrave initiation and use, including number of prescriptions, number of treatment episodes and duration between prescriptions, as well as estimating the number and percentage of patients compliant and non-compliant with the SmPC.

Analysis of compliance to the labelled indication and contraindications will be adapted to the specific SmPC for the country relevant to the data source (s). Examples of non-compliance include, but are not limited to:

Use inconsistent with labelled indication:

- 1. Age <18 years
- 2. Use other than management of weight
- 3. Management of weight in a patient who does not have obesity or is not overweight and has a weight-related comorbidity
- 4. A prescribed maintenance dose other than the Mysimba/Contrave 32mg/360mg
- 5. Continued use past 16 weeks without \geq 5% weight loss

Use in patients with contraindications:

- 6. A current diagnosis of uncontrolled hypertension, seizure disorder (or history of seizures), or end-stage renal failure
- 7. A history of bipolar disorder, anorexia nervosa or bulimia
- 8. A current dependence on chronic opioids or opiate agonists (e.g., methadone)
- 9. A current state of acute opiate withdrawal
- 10. Any concomitant treatment containing bupropion, naltrexone, or a MAOI
- 11. Patients with a known central nervous system tumour

Proprietary and Confidential:

- 12. Patients undergoing acute alcohol or benzodiazepine withdrawal
- 13. Patients with severe hepatic impairment (dependent on local SmPC)

The secondary objectives of this study are:

- 1. To assess and compare the observed incidence of AESIs in usual clinical practice among users of Mysimba/Contrave compliant and non-compliant with the SmPC. AESIs include new onset of the following:
 - 1. Seizures
 - 2. Suicidality (i.e., suicidal ideation, attempted suicide or completed suicide)
 - 3. Neuropsychiatric events (i.e., mania or depression)
 - 4. Hepatotoxicity
 - 5. Severe hypersensitivity reaction
 - 6. Serotonin syndrome

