9.7.2. Descriptive Statistics

For demographic and baseline variables and duration of Mysimba/Contrave use (measured as both continuous treatment of the initial Mysimba/Contrave duration and the total treatment duration of Mysimba/Contrave), descriptive statistics will be used to describe continuous variables, (e.g., mean, standard deviation, median, quartiles 1 and 3, minimum, maximum, and two-sided 95% confidence intervals [CI]). Categorical variables will be described by the total and percentage of each response and the number of missing data (data that are unavailable in the database).

Patterns of Mysimba/Contrave use will be described by mean (standard deviation, SD) and median (quartile1, quartile 3) number of prescriptions per patient, number and duration of treatment episodes per patient as well as the average duration between prescription episodes. Analyses will be performed for all users of Mysimba/Contrave, including an assessment of whether the subjects have adhered to the prescribed treatment with Mysimba/Contrave according to the terms of the SmPC (adapted to the local country SmPC for the data source as needed, and adapted if BMI is not accessible). The number and proportion of patients who received treatment with Mysimba/Contrave will be provided according to the following subgroups (availability of variables to be summarized in SAP):

(a) Inconsistent with labelled indication:

- 1) Age < 18 years
- 2) Use other than management of weight
- 3) Management of weight in a patient who does not have obesity or is not overweight and has a weight-related comorbidity
- 4) A prescribed maintenance dose other than the Mysimba/Contrave 32mg/360mg
- 5) Continued use past 16 weeks without \geq 5% weight loss
 - (b) Incompatible with the stated contraindications set out in the SmPC:
- 1) A current diagnosis of uncontrolled hypertension, seizure disorder (or history of seizures), or end-stage renal failure
- 2) A history bipolar disorder, anorexia nervosa or bulimia
- 3) A current dependence on chronic opioids or opiate agonists (e.g., methadone)
- 4) A current state of acute opiate withdrawal
- 5) Any concomitant treatment containing bupropion, naltrexone, or a MAOI
- 6) Patients with a known central nervous system tumour
- 7) Patients undergoing acute alcohol or benzodiazepine withdrawal
- 8) Patients with severe hepatic impairment

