9.7.3. Incidence Rate of AESIs

The incidence rate of AESIs per person-years of exposure after initiation of Mysimba/Contrave will be assessed. Person-time of exposure will be calculated as the duration from the index date through the date of last Mysimba/Contrave prescription or dispensation (i.e., total treatment duration of Mysimba/Contrave), as applicable, plus 4 weeks. The number of cycles of Mysimba/Contrave during the exposure period will be summarized comparing all users, irrespective of their treatment duration status.

For each type of AESI, the crude incidence of new AESIs will be reported and the incidence proportion and 95% CI of will be estimated as the number of patients experiencing each type of event during Mysimba/Contrave exposure divided by the number of patients initiating treatment with Mysimba/Contrave. The proportion will be reported per 1,000 persons. The incidence density rate and 95% CI of AESI will be reported per 1,000 per person-years, using the sum of the person-years of the at-risk population as the denominator.

Further, clinical events of interest that might be associated with the occurrence of a potential AESI (e.g., newly initiating anti-epileptic/seizure medication, newly initiating medications indicated for mania or depression) will also be tabulated. For hepatotoxicity, liver function tests can be used (when available) in addition to diagnostic codes.

For reason(s) patients who discontinue treatment (i.e., do not refill their prescription), clinical events and health status occurring within the 90-day window prior to discontinuation will be summarized.

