9.7.3.1. Incidence Rates of AESIs in Subgroups of Patients

If data are available and appropriate predictors are available in the respective database, sensitivity analyses around the definition of each type of AESI will be performed. Incidence proportion and density of each type of AESI will also be calculated for the subgroup of patients compliant or non-compliant with the EU SmPC (as listed in section 9.7.1, the criteria will be adapted for the relevant country of the data source stems if the SmPC differ across such countries, i.e., for U.S.), including relevant comorbidities, concomitant medications, and pregnancy. Adaptations will be made if BMI is not available; these will be described in the SAP. The incidence rate (and 95% CI) of new onset comorbidities and concomitant medication after initiation of Mysimba/Contrave will be assessed. Incidence rates will be determined both for the person-years of time exposed to Mysimba/Contrave (i.e., while patient taking medication) after the index date as well as for all person time through 548 days after the index Mysimba/Contrave prescription.

The incidence rate (and 95% CI) of pregnancy and breastfeeding after the Mysimba/Contrave index date will be assessed among females initiating Mysimba/Contrave. These analyses will be conducted in data sources where the necessary variables are present.

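### The comparison of new-onset AESIs conflicts, for seizures, with a non-compliant group partly defined by past seizures, and the numerator and denominators do not settle who counts

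*Protocol*

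**What the plan says.** Secondary objective 1 in Protocol section 8 is "To assess and compare the observed incidence of AESIs in usual clinical practice among users of Mysimba/Contrave compliant and non-compliant with the SmPC". The same item adds that "AESIs include new onset of the following" and lists seizures, suicidality, mania or depression, hepatotoxicity and others. Section 9.7.3 likewise speaks of new AESIs. New onset is not defined.

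The non-compliant group is built from label criteria, some of which are medical history. Sections 8 and 9.7.2 include "seizure disorder (or history of seizures), or end-stage renal failure". Section 8 also has "A history of bipolar disorder, anorexia nervosa or bulimia", and severe hepatic impairment where the local label lists it. Other routes have nothing to do with a prior AESI, for example "Any concomitant treatment containing bupropion, naltrexone, or a MAOI". Section 9.1.2 applies no exclusions.

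In section 9.7.3 the incidence proportion is the number of patients with each type of event during exposure, "divided by the number of patients initiating treatment with Mysimba/Contrave". The incidence density uses the person-years of an at-risk population that is not defined. Section 9.7.3.1 carries both measures into the comparison: "Incidence proportion and density of each type of AESI will also be calculated for the subgroup of patients compliant or non-compliant".

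Appendix 2 gives one code for seizures (G40) and no separate code for seizure disorder. It gives one list for hepatic impairment (K70, K72-K75) and no separate hepatotoxicity list. Mania is F30 and bipolar disorder F31.

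**The concern.** For seizures, the same fact does two jobs. A past seizure puts the patient in the non-compliant group and, if new onset means first onset, also disqualifies any later seizure as an outcome. Because the proportion is divided by all initiators, the patient still adds to the denominator. The seizure risk of patients with a seizure history then cannot show up in the seizure comparison.

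Sections 4 and 7 say the study is to inform whether the SmPC should be revised. A seizure comparison that tends towards or below 1 by construction could be read as reassurance about contraindicated use.

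**Working it through.** **The plan's own figure.** The protocol gives no figure for this point: no prevalence of seizure history, no recurrence risk and no expected ratio. Its zero-event bound in section 9.5 (3 in 3,000, or 0.1%) does reproduce: 1 − 0.05^(1/3000) = 0.0998%. It does not bear on this point.

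**Reading 1: first onset.** This follows the new-onset wording of section 8 and the new-AESI wording of section 9.7.3. Assumptions:
- a share *f* of the non-compliant group has a prior seizure;
- those patients have *k* times the seizure risk of event-free patients;
- all other risks are equal in the two groups, and the compliant group has no recorded seizure history, because such a history would make the patient non-compliant.

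The non-compliant/compliant risk ratios are then:
- all on-treatment seizures: (1 − *f*) + *f·k*;
- first onset over all initiators: 1 − *f*;
- first onset over event-free patients only: 1.0;
- share of the non-compliant group's seizures not counted: *f·k* / [(1 − *f*) + *f·k*].

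| *f* | *k* | All seizures | First onset, all initiators | First onset, event-free only | Share not counted |
|---|---|---|---|---|---|
| 5% | 5 | 0.95 + 0.25 = 1.20 | 0.95 | 1.00 | 21% |
| 5% | 10 | 0.95 + 0.50 = 1.45 | 0.95 | 1.00 | 34% |
| 10% | 10 | 0.90 + 1.00 = 1.90 | 0.90 | 1.00 | 53% |
| 20% | 10 | 0.80 + 2.00 = 2.80 | 0.80 | 1.00 | 71% |

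The two first-onset columns do not depend on *k*: whatever the recurrence risk, it leaves no trace in the ratio. Over *f* from 2% to 40% and *k* from 1 to 50, the share not counted runs from 2% to 97%. These inputs are illustrative only.

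**Reading 2: any post-index event.** Section 9.7.3 counts patients who experience each type of event during exposure, and section 9.3.2 summarises the occurrence of AESIs from diagnostic codes. Neither numerator mentions history. Here a recurrent seizure counts, and all initiators is a matching denominator. But G40 has to serve for both history and outcome. If a share *c* of history patients receive a repeat G40 code without a seizure, and event-free patients have risk *r*, the ratio becomes (1 − *f*) + *f*(*k* + *c*/*r*). When *r* is small, even a modest *c* inflates the ratio. The bias now runs the other way.

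**Does the look-back separate the readings?** Section 9.3.3 sets 365 days for baseline variables unless stated otherwise, and gives no other window for history of seizures. If history and new onset share that window, the patients flagged as contraindicated are exactly those barred from a first onset. Some could contribute only if history is searched further back than new onset, which the protocol does not say. Appendix 3 rates seizure as available in all four Nordic countries but seizure disorder as unlikely, so Nordic status will rest largely on the same variable as the outcome.

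**Other pairs.** Severe hepatic impairment and hepatotoxicity may overlap because there is one liver code list, but the criterion is narrow and depends on the local label, and liver tests may be used where available. Bipolar disorder and mania overlap weakly: a patient with F31 can still have a first F30 or depression code, unless the analysis treats F31 as a prior event.

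**The case against.** The strongest reply is that new onset may simply mean new after initiation. The numerator sentence in section 9.7.3 and the occurrence wording in section 9.3.2 then count a recurrent seizure, and all initiators is the right denominator. Washout and at-risk rules are commonly left to a statistical analysis plan, which is not shown here, and section 9.7.3.1 foresees sensitivity analyses of AESI definitions where data allow. Restricting to new onset is also a recognised guard against counting follow-up codes for old disease.

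Much of this stands. The protocol does admit an any-event reading, so a first-onset count is not certain. But the new-onset restriction, the group definition and the all-initiator denominator are all fixed in the protocol and pull against each other there. The any-event reading brings its own bias, and the conditional sensitivity analyses do not commit to reporting events by prior history.

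A reader might go further and infer that contraindicated patients cannot contribute the events they are contraindicated for, across seizures, mania and liver events. The documents do not support that. The block depends on the reading, applies only to the same event, and is weak for bipolar disorder. A patient with past seizures can still contribute a cardiovascular event or suicidality, and patients non-compliant for unrelated reasons can contribute every AESI. Nor do the documents say that patients with a history are dropped from the density; if they are, that rate is an ordinary first-event rate with matching parts.

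This is also a secondary, descriptive comparison with no a priori hypothesis and, by Appendix 1, no measure of association. That limits the weight of the point but does not remove it, because the objective is expressly to compare.

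**Conclusion.** The point holds for seizures. On a first-onset reading, the non-compliant/compliant ratio of proportions is pulled to 1 − *f*, and a density restricted to event-free patients gives 1.0, whatever the true recurrence risk. On an any-code reading, carried-forward G40 codes can push the ratio up. The protocol supports both readings, so even the direction of the bias is open. The point is possible for hepatic events where the local label makes severe hepatic impairment a contraindication, and weak for bipolar disorder and mania.

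The size cannot be derived from the documents. The table rests wholly on assumed *f* and *k*, equal risks otherwise, and no recorded seizure history in the compliant group. A reader might infer that the study will show contraindicated use to be as safe as or safer than compliant use overall; that does not follow, because the distortion is confined to the same event and to one of the two readings.

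**What to change.** In Protocol sections 8 and 9.7.3:
- State for each AESI whether the outcome is first onset or any post-index event, and give the look-back used to establish history.
- Use the same patients in numerator and denominator, for both the proportion and the rate, and define the at-risk population accordingly.
- Within the compliant and non-compliant groups, report on-treatment events separately for patients with and without a prior history of that event. Keep new onset as the no-history stratum, with its own denominator. For seizures, where both use the same look-back, the history stratum falls wholly in the non-compliant group and should be read on its own.
- If an acute contact (inpatient or emergency diagnosis) is required in order to screen out follow-up codes, apply it identically in both strata, or use it only as a sensitivity analysis. Otherwise the event would mean different things in the two strata.

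The cost is wording plus one extra stratification, using data already collected. The history cells will be small, some may fall under the small-number masking in section 9.7.2, and some follow-up codes will still be counted as events in the history stratum.

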 - 7. Major adverse cardiovascular events (i.e., cardiovascular-related death, non-fatal myocardial infarction, or non-fatal stroke)

Deaths will also be reported in patients in which vital status is known.

- 2. To assess the proportions of patients in the following groups who are at increased risk for AESI and to describe the characteristics of the patients with AESI in these groups:
 - 1. Any user of Mysimba/Contrave
 - 2. Users compliant with SmPC
 - 3. Users out of compliance with SmPC, as described above
- 3. To assess the duration of Mysimba/Contrave use
- 4. To identify to the extent possible within the data sources:
 - 1. Initial titration scheme and proportion aligned with SmPC
 - 2. Dose adjustment in special populations and proportion aligned with SmPC
 - 3. Reasons for treatment discontinuation (not typically available in these databases)
 - 4. AESIs leading to treatment discontinuation (not typically available in these databases)

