9.3.2. Outcomes

When available, the following variables will be collected after initiation of Mysimba/Contrave (Post-Index Date). A draft listing of variables available in each country is included in Appendix 3 and will be included as final in the Statistical Analysis Plan (SAP).

Proprietary and Confidential:

This document cannot be used, distributed, or reproduced in any way without the prior written consent of Currax Pharmaceuticals LLC.

- 1. BMI, height, and weight prior to index date, the date of initiation of the medication(s) of interest, (obtained directly from data sources; BMI may be calculated if height and weight available). In the event that BMI and/or weight are not available through licensed access to the Scandinavian National Patient Registries, an attempt will be made to identify the obese population through diagnosis codes or procedures such as counseling for weight loss. It should be noted that this approach may identify a more obese and more motivated population than what would be identified on the basis of BMI. In addition, an approach may be implemented to predict BMI or apply published algorithms predicting BMI. Details will be laid out in the SAP.
- 2. Weight will be obtained if available 16-24 weeks post-index date to evaluate use inconsistent with labelled indication. BMI after index date will be obtained in the same timeframe, if available.
- 3. Relevant comorbidities (obtained via ICD-10 codes):
 - 1. Weight-related comorbidities (i.e., type 2 diabetes, dyslipidaemia, hypertension)
 - 2. Neuropsychiatric conditions (mania, bipolar disorder, major depressive disorder [MDD], anorexia nervosa, bulimia)
 - 3. Uncontrolled hypertension
 - 4. Moderate or severe renal impairment
 - 5. End-stage renal disease
 - 6. Seizure disorder
 - 7. Hepatic impairment (defined by Child-Pugh score category)
 - 8. Central nervous system tumour
- 4. Concomitant medication use, including: naltrexone, bupropion, CYP2B6 inhibitors, CYP2B6 inducers, CYP2B6 substrates, CYP2D6 substrates, drugs that lower seizure threshold, opioid or opiate agonist, or MAOI (obtained via ATC [outpatient, Nordic data] or NDC [US data])
- 5. Pregnancy status and breastfeeding status (obtained via ICD-10 codes)
- 6. AESIs (obtained via ICD-10 codes):
 - 1. Seizures

- 2. Suicidality (i.e., suicidal ideation, attempted suicide or completed suicide)
- 3. Neuropsychiatric events (i.e., mania or depression)
- 4. Hepatotoxicity
- 5. Severe hypersensitivity reaction

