Appendix 3. Variable Availability by Country (final list to be confirmed in SAP)

LEGEND: "--" indicates that the information is not available

Partial = may be available for some patients

Limited = anticipated to be underreported

Yes = likely to be available if true for patient

Unlikely = available for some patients; may not be accurate

Calculated = assumptions can be used to derive a variable for this information

Variable	US	Denmark	Norway	Sweden	Finland
Mysimba prescription	Yes				
Date of Mysimba	Yes				
prescription					
Mysimba dispensing	Partial	Yes	Yes	Yes	Yes
Date of Mysimba	Partial	Yes	Yes	Yes	Yes
dispensing					
Mysimba dosage for each	Partial				
dispensing					
Initial titration scheme	Maybe				
Dosing of Mysimba during	Maybe				
titration					
Dose adjustment of	Partial				
Mysimba (e.g., for special					
population)					
Maintenance dose of	Maybe				
Mysimba					
Mysimba days' supply	Calculated	Calculated	Calculated	Calculated	Calculated
Date of	Partial	Yes	Yes	Yes	Yes
eligibility/enrolment					
available to identify					
continued					
engagement/recording of					
clinic visits					
Age	Yes	Yes	Yes	Yes	Yes
Sex	Yes	Yes	Yes	Yes	Yes
BMI	Partial				
Height	Partial				
Weight	Partial				
Diabetes	Yes	Yes	Yes	Yes	Yes
Dyslipidaemia	Yes	Yes	Yes	Yes	Yes

Proprietary and Confidential:

This document cannot be used, distributed, or reproduced in any way without the prior written consent of Currax Pharmaceuticals LLC.

Anorexia nervosa	Yes	Yes	Yes	Yes	Yes
Bulimia	Yes	Yes	Yes	Yes	Yes
Hypertension	Yes	Yes	Yes	Yes	Yes
Uncontrolled hypertension	Yes	Yes	Yes	Yes	Yes
Moderate or severe renal	Yes	Yes	Yes	Yes	Yes
impairment	1 68	1 68	1 68	1 68	1 68
End-stage renal disease	Yes	Yes	Yes	Yes	Yes
Seizure	Yes	Yes	Yes	Yes	Yes
Seizure disorder	Maybe	Unlikely	Unlikely	Unlikely	Unlikely
Hepatic impairment via	Maybe				
Child-Pugh score	Mayoc				
Hepatic impairment via diagnosis	Yes	Yes	Yes	Yes	Yes
Central nervous system	Yes	Yes	Yes	Yes	Yes
tumour					
Substance use/abuse	Limited	Limited	Limited	Limited	Limited
Acute opiate withdrawal	Limited				
Acute alcohol or	Limited				
benzodiazepine withdrawal					
Suicidality	Limited	Limited	Limited	Limited	Limited
Mania	Limited	Limited	Limited	Limited	Limited
Bipolar disorder	Limited	Limited	Limited	Limited	Limited
Major depressive disorder	Yes	Yes	Yes	Yes	Yes
Hepatotoxicity	Yes	Yes	Yes	Yes	Yes
Severe hypersensitivity reaction	Limited	Limited	Limited	Limited	Limited

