Cardiovascular-related	Partial	Partial	Partial	Partial	Partial
death	1 artiar	1 artiar	1 artiai	1 artiar	1 artiar
Non-fatal myocardial	Yes	Yes	Yes	Yes	Yes
infarction					
Non-fatal stroke	Yes	Yes	Yes	Yes	Yes
Use of naltrexone (other	Yes	Yes	Yes	Yes	Yes
than Mysimba)	Vaa	Vaa	Vac	Vac	Vaa
Use of bupropion (other than Mysimba)	Yes	Yes	Yes	Yes	Yes
, , , , , , , , , , , , , , , , , , , ,	Vac	Vac	Vac	Vac	Yes
Use of CYP2B6 inhibitor	Yes	Yes	Yes	Yes	
Use of CYP2B6 inducer	Yes	Yes	Yes	Yes	Yes
Use of CYP2B6 substrate	Yes	Yes	Yes	Yes	Yes
Use of CYP2Db substrate	Yes	Yes	Yes	Yes	Yes
Use of medicine that lowers	Yes	Yes	Yes	Yes	Yes
seizure threshold	Vac	V	V.	V	Var
Opioid or opiate agonist	Yes	Yes	Yes	Yes	Yes
prescription or dispensing					

MAOI prescription or	Yes	Yes	Yes	Yes	Yes
dispensing	1 05	1 05	1 05	1 05	105
Pregnancy	Yes	Limited	Limited	Limited	Limited
Breastfeeding	Limited	Limited	Limited	Limited	Limited
Death	Partial	Yes	Yes	Yes	Yes
Disenrollment	Partial	Partial	Partial	Partial	Partial
Socioeconomic data		Partial	Partial	Partial	Partial
Laboratory results	Limited	Limited	Limited	Yes	Limited
Surgical procedures	Yes	Yes	Yes	Yes	Yes
Diagnostic testing results	Limited	Limited	Limited	Yes	Limited
Indication (reason) for	Partial				
treatment with Mysimba					
Discontinuation and date of	Calculated	Calculated	Calculated	Calculated	Calculated
discontinuation of					
Mysimba					
Reason(s) for treatment	Partial-no				
discontinuation	attribution				
Discontinuation due to	Partial-no				
adverse event	attribution

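### MACE admits a fatal MI or stroke only through cardiovascular death, which the protocol rates as partly available in all five data sources, so MACE is likely undercounted

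*Protocol*

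**What the plan says.** Section 8 lists, as the seventh adverse event of special interest (AESI), "Major adverse cardiovascular events (i.e., cardiovascular-related death, non-fatal myocardial infarction, or non-fatal stroke"; Section 9.3.2 repeats the definition. Neither section has a component for MI or stroke regardless of survival. Section 9.3.2 finds these events by diagnosis code: "AESIs (obtained via ICD-10 codes". Section 8 adds a separate count: "Deaths will also be reported in patients in which vital status is known".

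Appendix 3 gives availability in the order US, Denmark, Norway, Sweden, Finland:

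- Cardiovascular death: "Cardiovascular-related Partial Partial Partial Partial Partial", where "Partial = may be available for some patients".
- Death from any cause: "Death Partial Yes Yes Yes Yes".
- Non-fatal stroke: "Non-fatal stroke Yes Yes Yes Yes Yes"; non-fatal MI is rated the same.

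Sections 9.4.1 (Nordic) and 9.4.2 (US) each say the data should suffice for every variable apart from a short list of exceptions. Cardiovascular death is in neither list.

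**The concern.** The definition splits MI and stroke by survival and sends the fatal ones to the component that the protocol itself rates as incomplete. The two components rated Yes everywhere cannot take them. The most severe events are thus the ones most exposed to loss, while the result keeps the MACE label.

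Two things are at stake. The incidence proportion and rate of MACE in each database would be too low. The first secondary objective also compares AESI incidence between users compliant and non-compliant with the SmPC, and that comparison would be distorted if the fatal share, or its capture, differed between the groups. The results are meant to inform risk management and possible revision of the SmPC.

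**Working it through.** **Where each kind of event goes under the definition as written**

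| Event | Record available | Component |
|---|---|---|
| MI or stroke, patient survives | code | non-fatal MI or stroke: counted |
| Fatal MI or stroke | code, death and usable cause | cardiovascular death: counted |
| Fatal MI or stroke | code and death, no usable cause | none: lost |
| Fatal MI or stroke | code, death not recorded (possible in the US) | non-fatal: misclassified but counted |
| Cardiovascular death without an MI or stroke code | usable cause | cardiovascular death: counted |
| Cardiovascular death without an MI or stroke code | no usable cause | none: lost |

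The two lost rows need cause of death to be missing for some patients, which is what the Partial rating means. In the Nordic sources death itself is rated Yes, so survival can be established and the gap is cause of death alone. In the US death is also Partial, so both the third and the fourth rows can occur.

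**The plan's one precision figure that could apply to MACE.** Section 9.5 says that no events among 3,000 patients bounds the risk at 3 in 3,000 with 95% confidence. Check: 1 − 0.05^(1/3000) = 0.000998, or 0.998 per 1,000. The figure is reproduced and is not in dispute, but it presumes that every event is captured.

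**Illustration only.** Let f be the share of true MACE that is fatal and c the share of fatal events that still reach MACE by any route. The share lost is f × (1 − c). The documents give neither f nor c; the values below are assumptions.

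- f = 0.10, c = 0.75: 0.10 × 0.25 = 2.5% lost
- f = 0.20, c = 0.50: 0.20 × 0.50 = 10% lost
- f = 0.30, c = 0.50: 0.30 × 0.50 = 15% lost
- f = 0.50, c = 0.25: 0.50 × 0.75 = 37.5% lost

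At 10% lost, sensitivity is 0.90 and the zero-event bound on true risk becomes 0.998 / 0.90 = 1.11 per 1,000. At 37.5% lost it is 0.998 / 0.625 = 1.60 per 1,000.

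**Comparison between compliance groups, also assumed.** Suppose there is no true difference, c = 0.50 in both groups, and f is 0.10 in one and 0.30 in the other. The observed ratio is (1 − 0.15) / (1 − 0.05) = 0.85 / 0.95 = 0.89 instead of 1.00. With equal f and c in the two groups the ratio is unaffected.

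**The case against.** The strongest reply is that this is a conventional composite, that the protocol sets no survival window and no rule for dropping a coded MI or stroke, and that such details belong in the SAP. Appendix 3 is a draft to be confirmed there, and Section 9.4.2 leaves fuller description of the US database to the US SAP. This stands as far as missing detail goes: the absence of a named US cause-of-death source is not a defect of the protocol. It does not remove the point, because the composite is already fixed in Sections 8 and 9.3.2. Whatever window is chosen, an MI or stroke that kills the patient is not non-fatal.

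A reader might infer more than the documents support:

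- **That the loss is greatest in the US.** This is not shown. An unrecorded US death leaves the coded MI or stroke in MACE as non-fatal.
- **That US and Nordic MACE will be pooled or formally contrasted.** Section 9.7.1 plans separate analyses by country with a synthesis across the Nordic databases, and Section 9.4.2 puts the US in its own report.
- **That capture differs between compliant and non-compliant users.** Nothing in the protocol says so; the ratio of 0.89 is conditional on assumed values.

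It is also fair to say that deaths are already reported where vital status is known, that Section 9.4.1 mentions linkable death registries, and that Section 9.9.1 concedes that diagnoses not tied to a medical encounter may be missed. A separate death count does not return lost events to MACE. The Section 9.9.1 sentence does not cover a coded event that the definition itself excludes.

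**Conclusion.** The point holds. By the protocol's own ratings, the MACE definition can lose fatal events in every database, through the two routes shown. The direction is an undercount; the size cannot be computed from the documents. A figure such as 10 to 40% is tempting: a fatal share of 20 to 40% with none to half captured gives 0.20 × 0.50 = 0.10 up to 0.40 × 1.00 = 0.40. Both inputs are assumed, and the upper end needs no fatal event ever to be captured, which conflicts with the Partial rating. Other assumed inputs give 2.5 to 37.5%.

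Sections 9.4.1 and 9.4.2 also disagree with Appendix 3, since neither lists cardiovascular death as an exception.

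The documents do not require dropping MACE as the US cardiovascular outcome in favour of MI or stroke alone. That is a debatable choice, and the remedy does not depend on it.

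**What to change.** 1. In Sections 8, 9.3.2 and 9.7.3, define MACE as any coded MI or any coded stroke, fatal or not, or cardiovascular death where the cause is available. With complete cause of death, and deaths from MI and stroke classed as cardiovascular, this gives the same composite as now. With incomplete cause of death it recovers the coded events that would be lost, and it no longer depends on showing survival.
2. In each database where cause of death is incomplete, add one row for MI, stroke or all-cause death among patients with known vital status, as an upper bound against the loss of fatal events, and label MACE a likely undercount. This row covers the uncoded cardiovascular deaths that step 1 cannot recover.
3. Add cardiovascular death to the exceptions in Sections 9.4.1 and 9.4.2 so that they agree with Appendix 3.

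The cost is the wording and one table row per affected database. The downside is that the bound includes non-cardiovascular deaths, so it will overstate MACE and should be presented only as a bound.
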